Various reviews have shown that 1 hydroxy pyrene (1-OHP) is a biomarker of exposure to poly-cyclic aromatic hydrocarbons from traffic related air pollution (161, 162). 1 hydroxy pyrene is a major metabolite of pyrene and it is used to estimate overall exposure to PAH. Work specifically on taxi drivers has shown that urinary 1 OHP levels were increased in drivers compared with non-occupationally exposed subjects. Elevated 1-OHP levels were also shown to be associated with elevated levels of pro-inflammatory cytokines and were negatively associated with levels of antioxidants in exposed taxi drivers. (163). In DRIIVE we look to show the impact of use of a HEPA filter on 1 OHP levels in drivers by sampling levels pre-and post implementation of filter.

PRELIMINARY STUDIES

Immigrant Health and Cancer Disparities Service (IHCD)

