4.1 OVERVIEW OF STUDY DESIGN/INTERVENTION

4.2 Design

This study is proposed to be carried out across a two year period including an intervention period and dissemination of results to the Taxi Network community. Twenty eight non-smoking male NYC cab drivers will be recruited and randomized to one of two study arms, an Intervention Group (to receive the HEPA filter 2 weeks into their 4 week period of participation) and a Wait-list Control Group (to receive the HEPA filter at the end of their 4 weeks of participation). For the Intervention and Wait-list Control Group drivers, during the first 2 weeks, measurements (e.g. biological markers and air monitoring) will be taken under usual conditions. At the end of the initial two weeks, portable HEPA air purifiers (136) will be placed in the Intervention Group drivers' cars and the air monitoring and biological parameters will be repeated for another 2-week period, to determine changes in PM levels and physiological measurements as a result of this targeted intervention. The Wait-list Control Group drivers will not receive a HEPA air purifier at this time, but will also have the air monitoring and biological parameters repeated for another 2 weeks. At the end of the 1 month period of measurements for both groups of drivers, the Wait-list drivers will then receive a HEPA air purifier, so that they may also potentially benefit from the intervention being tested in this study, but no further measurements will be taken. Drivers will serve as their own controls before/after work and before and after the intervention.

Our taxi network CAB (Community Advisory/Action Board) will be engaged in the implementation and dissemination of the proposed study. This Taxi CAB represents the full range of the taxi driver experience, including varied shifts, income, education, age, ownership/lease arrangements, and countries of origin. The Taxi CAB will be instrumental in study recruitment and dissemination of results. The CAB will meet quarterly, with additional meetings as needed. This study is conducted in collaboration with Drs. [name] and [name]'s research teams at New York University Department of Environmental Medicine, and [name], working from the City College of New York (CCNY). Biological specimens collected will be immediately transported to MSK BAIC Core facilities for temporary storage and will be shipped later to either NYU or CCNY (outlined in the assessment and evaluation-section 7).

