4.3 Intervention

Over the course of the study, we will monitor several biological and physiological markers associated with lung cancer and CVD risk, along with ongoing air monitoring of work-sites and residences of all study participants. HEPA filters were selected as the intervention because of their effectiveness in removing PM and volatile organic compounds (VOCs), ease of use, relatively low-cost, small size, light weight, and lack of interference with drivers' normal practices (136). In a previous study by Pui et al., placing the air recirculation mode on (and with a cabin air filter in place already installed by the car manufacturer, not all cars have cabin air filters), was successful at substantially removing ultrafine particles, although was still relatively inefficient (45.5% particle removal efficiency) compared to a HEPA filter (137).

The study will require 4 weeks of participation. Drivers will be recruited and randomized to either the control condition or the HEPA filter intervention condition. The in-vehicle (for all drivers PM exposure levels and physiologic and biochemical markers will be measured over the course of 1 month. For the first two weeks of the 1-month period, measurements will be taken under usual conditions (*without HEPA filters*) for all participants.

Particulate matter concentrations will be measured/monitored through *Personal DataRams* (pDR) (*personalDataRam*[™] model pDR-1200). The DataRam measures particulate matter through optical impedance, and produces per-minute averages. Therefore, the time that the DataRam is —onll will be directly reflected in the data that is produced. The pDR is 24 ounces, 6.3 inches in height, 8.1 inches in width, and 2.4 inches in depth, and is thus very portable. One pDR will be provided to each enrolled participant. All participants will monitor PM at their homes in the room in which they spend most of their off work hours; the DataRam will then be moved to the bedroom at night (or during sleeping hours). For drivers, the pDR will record PM levels throughout the work shift while the vehicle is in motion, momentarily stopped, or parked.

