Black carbon exposures will be measured/monitored through BGI 400 Personal Sampler Pump. The BGI pump is a constant air flow sampler that has broad applications in industry hygiene and environmental testing. It is compact, 6.75 inches in height, 3.1 inches in width and 2.3 inches in depth, which is ideal for mobile projects. It is attached to an external

Nickel Metal Hydride battery, which is 5.75 inches in height, 3.60 inches in width and 1.10 inches in depth. BGI pump connects with a Tygon or ID tubing, ¼ inch in diameter, which is attached to a plastic cassette on the other end, where the pre baked quartz filter is placed. The BGI pump and filter will be placed in the vehicle of the participant at the beginning of their work shift and picked up at the end of their shift. All participants will monitor black carbon exposures at minimum for one work shifts on week 1 and week 4 of the study, or a maximum of three work shifts every week.

PAH exposure will be measured through portable passive Polyurethane Foam Filter (PUF) sampler sized 10 cm by 2.2 cm diameter (171). The PUF filter will be place in the vehicle of the drivers at the beginning of their work shift and picked up at the end of their shift. Drivers will monitor PAH through PUF sampler one day every week.

The intervention of HEPA air filters will be introduced after 2 weeks of participation in the Driver Intervention group (but not in those of the control drivers' cars. The HEPA air purifier is 7.5"x 8.5", 6 lb, and covers up to 150 sq feet. An accompanying auto adapter kit contains a cigarette lighter adapter, 7 foot cord, and a seatbelt clip to secure the filter (159). Air monitoring and measurements of PM exposure levels and physiologic and biochemical markers will be continued for another 2-week period to assess the extent of risk reduction achieved by this targeted intervention. Two weeks should be more than sufficient to measure risk reduction by the HEPA filter intervention, as the study by Pui et al. showed that with the air recirculation mode on and a cabin filter in place, in-cabin aerosol concentration was reduced to below typical office air concentrations in approximately 3 minutes (137). HEPA filters will be given to drivers in the Wait-list Control Group at the end of the 4 weeks of participation.

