11.0 BIOSTATISTICS

Overview. This pilot study follows a two parallel arm design. Drivers will be randomized to one of two groups, an Intervention Group (an in-vehicle HEPA filter will be provided) and a Wait-list Control Group (HEPA filter will be provided at the end of wait-list period). We plan to recruit a sample of n=14 participants in each group (n=11 per arm with analyzable (non-missing) data, assuming a 25% drop-out rate as described below).

General analytic strategies. The general data analytic paradigm for this pilot study will be descriptive statistics only. The aim is to collect pilot data to help guide a future randomized intervention study. Descriptive statistics and assessments of correlations will be sought to address the aims (see below). The sample size of 14 per condition was primarily determined by resources limitations. A sample of 14 per condition was deemed possible within the funding resources of no more than 2 years.

Analytic plans for the Specific Aims.

Aim 1a: The primary aim will be to collect preliminary data on in-vehicle excess PM exposure.

Descriptive statistics (means and standard deviations) will be sought on: 1) PM size distribution 2) mass concentration, and 3) chemical composition for all three groups. These observations will be used to evaluate to what extent the two groups were exposed to these environmental hazards. For each study participant, an area-under-the-curve (AUC) summary will be sought for each of the three PM measurements over appropriate time periods. Generally, a daily average will be calculated from the hourly PM assessments. Then the AUC of the 28 daily averages will be calculated per person to represent the summary of PM exposures during study participation.

Aim 1b: To conduct a preliminary assessment of the correlation between PM exposure and physiologic and biochemical markers associated with increased risk of lung cancer and/or CVD.

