For each group, a correlation matrix will be constructed between the three components of the AUC outcomes described in Aim 1a and a set of physiologic and biochemical markers. Generally, Pearson's correlation coefficients will be sought. If preliminary analyses found the variables to be skewed, then Spearman's rank correlation coefficients will be calculated instead. The purpose of these correlation coefficients are to examine the associations between the environmental exposure to air pollutants and physiologic and biochemical markers. Point-biserial correlation coefficients will be sought between the continuous AUC summaries of PM data and other binary variables of interest (e.g., methylation). These correlation coefficients can be sorted in descending order to help identify the top candidates of physiologic and biochemical markers that are most likely to be associated with PM exposure. Care will be taken to match the variables by time, using the time stamps from the PM measurements and the date of biomarker serum collection. For example, the AUC of PM in the first week will be associated with serum cytokines measured during the first week. This work will have to be done in a post-hoc manner, after we have all data sources. Then we will evaluate the best strategies to link them together by time. It helps to have automatic time stamps by the PM measurement devices, which is likely to minimize coding errors and missing data.

Aim 2: To use a randomized wait-list controlled design to conduct a pilot study of whether a targeted intervention, installation of a portable car high-efficiency particulate air (HEPA) filter (to remove PM), results in a reduction of in-vehicle PM exposure and associated physiologic and biochemical markers among taxi drivers..

We will calculate the difference in the three PM components and in physiologic/biochemical markers between the HEPA intervention condition and the Wait-List Control condition to obtain the pilot data needed for a future, larger study with the potential to provide remediation to potential harmful exposures to air pollution among NYC taxi drivers.

Aim 3: To collect feasibility data on conducting the proposed randomized wait-list controlled pilot study among New York City taxi drivers.

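### Aim 2 names no time window and gives no role to the two unfiltered weeks, although the design describes a before/after, own-control comparison

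*Combined protocol and SAP*

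**What the plan says.** Section 11.0 gives Aim 2 a single analytic sentence: "We will calculate the difference in the three PM components and in physiologic/biochemical markers between the HEPA intervention condition and the Wait-List Control condition". Section 4.3 uses the word condition for the randomized arm, so this is a comparison between arms. No weeks, baseline, change score or adjustment are named.

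The design text goes further. All drivers are measured for two weeks without a filter and then for two more weeks, with the filter installed at the midpoint in the intervention arm only. Section 4.2 says the repeat measurements are "to determine changes in PM levels and physiological measurements as a result of this targeted intervention" and adds: "Drivers will serve as their own controls before/after work and before and after the intervention". Section 4.3 says measurements "will be continued for another 2-week period to assess the extent of risk reduction achieved by this targeted intervention". Section 3.0 plans to study urinary 1-OHP "by sampling levels pre-and post implementation of filter".

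The PM summary that Section 11.0 does define belongs to Aim 1a: "an area-under-the-curve (AUC) summary will be sought for each of the three PM measurements over appropriate time periods", followed by "Then the AUC of the 28 daily averages will be calculated per person to represent the summary of PM exposures during study participation". Matching by time is discussed only under Aim 1b, for correlations, and is left to be settled after the data are in.

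**The concern.** Aim 2 is the study's only randomized contrast, and its stated purpose is to supply pilot data for a larger trial. As written, the sentence could mean a difference in weeks 3-4, a difference in change from weeks 1-2, or a difference in some whole-study summary. These give different numbers.

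With about 11 analyzable drivers per arm, the arms can differ noticeably by chance before any filter is installed. Part of such a gap carries through into an unadjusted filter-on difference. The pre-filter data that could remove that part are already being collected. The residual SD and the pre/post correlation, both useful for sizing the next trial, are not requested.

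There is a related gap for PM. Aim 2 concerns in-vehicle exposure, but one DataRam per driver moves between cab and home (Sections 4.3 and 7.1). Section 11.0 gives no rule for separating the two.

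**Working it through.** **Inputs from the documents.** Section 11.0: 14 recruited per arm, 25% drop-out, 11 per arm analyzable, descriptive statistics only. Sections 4.2 and 4.3: two unfiltered weeks, then two weeks with the filter in one arm. No alpha, power, SD or pre/post correlation is given.

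**The plan's own figure.** 14 × (1 − 0.25) = 10.5, which rounds to the stated 11.

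**Assumption.** The correlation ρ between a driver's pre-filter and filter-on values is not in the documents. Values of 0, 0.3, 0.5 and 0.7 are used. Results are in units of one between-driver SD, with drivers treated as independent.

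**Chance gap before the filter.** SE = √(2/11) = 0.426 SD. The probability that the gap exceeds 0.5 SD in either direction is 0.241, so about 24% of randomizations.

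**Unadjusted filter-on difference.** SE = 0.426 SD. The 95% half-width is 2.086 × 0.426 = 0.889 SD (t on 20 df).

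**ANCOVA on the pre-filter value.** Average SE ratio to unadjusted = √[(1 − ρ²) × 19/18], where 19/18 is the average cost of estimating the slope. Half-width = 2.093 × 0.426 × ratio (t on 19 df).

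| ρ (assumed) | SE ratio | Change in SE | 95% half-width (SD) |
|---|---|---|---|
| 0 | 1.027 | about 3% larger | 0.917 |
| 0.3 | 0.980 | about 2% smaller | 0.875 |
| 0.5 | 0.890 | about 11% smaller | 0.794 |
| 0.7 | 0.734 | about 27% smaller | 0.655 |

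**Downside at ρ = 0 for a given chance gap d.** SE inflation = √[(2/11 + d²/20)/(2/11)], which is 1.034 at d = 0.5 SD and 1.095 at d = 0.85 SD.

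**Difference in change scores, for comparison.** SE ratio = √[2(1 − ρ)] = 1.18, 1.00 and 0.77 at ρ = 0.3, 0.5 and 0.7. A change score fits the own-control wording, but it is worse than ignoring baseline when ρ is below 0.5.

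**Which outcomes have a pre/post pair (Section 7.1).**
- PM, heart rate variability and blood pressure are measured in every week.
- Cytokines and white cells are sampled on one work day in week 1 and one in week 4.
- 1-OHP is sampled at the end of week 1 or 2 and again at the end of week 4.
- PUF samples are weekly. Black carbon is sampled at least in weeks 1 and 4.
- Methylation is taken at intake only, so it has no post-filter value.
- hs-CRP is at intake and at the end of the month in the text, but at intake only in the schedule table.

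**The case against.** The strongest reply is that this is a descriptive pilot sized by resources, that Section 9.1 does not list the HEPA effect as a primary outcome, and that the combined document already states a before/after intention. All of that stands. A reader might infer that the plan rejects the before/after comparison; Sections 3.0, 4.2 and 4.3 show that it does not. What is missing is the estimator. A reader might also infer that the Aim 2 estimate would be biased. Randomization keeps an unadjusted filter-on difference unbiased, and no test decision depends on it.

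Two larger effects are tempting and are not supported.
- If the Aim 1a 28-day AUC were used for Aim 2, a constant effect on the daily average would be halved (14 of 28 days). The plan never assigns that summary to Aim 2, and Aim 1a allows other windows.
- Averaging eight blood pressure readings per period might seem to promise an SE cut of 23% to 35%. That requires readings weeks apart to correlate as strongly as readings in the same period (assumed 0.2 or 0.3). With 0.3 within a period but 0.15 or 0.20 across periods, also assumed, the cut is about 5% or 12%. Half of the eight readings also come from days off work.

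Three further points stand as limits.
- Randomization follows consent and registration (Sections 6.0 and 12.3), so weeks 1-2 precede the filter but follow allocation. No blinding is described, and drivers who know their arm could behave differently in those weeks.
- Section 6.0 has driver pairs take part at about the same time to avoid seasonal PM differences. If pairs span the arms, which is not stated, both the chance gap and the gain for PM may be smaller than shown.
- The log-book items listed in Section 7.1 do not include shift start and end times, although Appendix C may capture them.

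**Conclusion.** The point holds as a gap in the Aim 2 estimator: no window is stated, and the pre-filter data have no stated use in the estimate, against a design that describes one. The consequence is a less precise pilot estimate, and one whose definition would be chosen after the data are seen.

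The size depends on a correlation that the documents do not give. The SE reductions of about 2%, 11% and 27% are for assumed values of 0.3, 0.5 and 0.7 with 11 independent drivers per arm. For cytokines, 1-OHP and other outcomes sampled on one day per period, the gain may be near nil. The average cost if the correlation is zero is about 3%. This is an inexpensive improvement worth making; it does not correct an invalid analysis.

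**What to change.** Add one paragraph to Section 11.0, Aim 2.

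- **Estimate.** For each outcome measured both before and after filter installation, take the between-arm difference, by randomized arm, in the filter-on period: weeks 3-4, or week 4 where only that exists. Adjust by ANCOVA for the same driver's pre-filter value: weeks 1-2, or the first sample.
- **Reporting.** Keep it descriptive: the estimate, its 95% CI, the residual SD and the pre/post correlation. Show the unadjusted filter-on difference alongside, because weeks 1-2 follow an allocation for which no blinding is described.
- **PM.** Use cab hours only, identified from device time stamps and recorded shift times, and confirm that the log captures shift start and end. State a rule for mixed hours. One option is to count an hourly average only if the whole hour lies within the shift, which keeps 9 of 10 or 11 of 12 hours when a shift starts mid-hour. Another is to use finer data if retained, since Section 4.3 says: "The DataRam measures particulate matter through optical impedance, and produces per-minute averages". State that the 28-day AUC serves Aim 1a only.
- **Blood pressure.** Use work-day readings, or report work-day and non-work-day readings separately.
- **Exclusions.** Leave out intake-only methylation. Include hs-CRP only once the Section 7.1 text and its schedule table are reconciled on an end-of-study sample.
- **Pairs.** State whether driver pairs span the arms.

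The essential step is to fix the window and the use of baseline; ANCOVA is the recommended form. No new sampling is needed. If shift times are not already logged, the log-book needs that entry. The statistical cost is an SE about 3% larger on average if the pre-filter value turns out to be uninformative.

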12.1 RESEARCH PARTICIPANT REGISTRATION AND RANDOMIZATION PROCEDURES

12.2 Research Participant Registration

Confirm eligibility as defined in the section entitled Criteria for Patient/Subject Eligibility.

Obtain informed consent, by following procedures defined in section entitled Informed Consent Procedures.

During the registration process registering individuals will be required to complete a protocol specific Eligibility Checklist.

The individual signing the Eligibility Checklist is confirming whether or not the participant is eligible to enroll in the study. Study staff are responsible for ensuring that all institutional requirements necessary to enroll a participant to the study have been completed. See related Clinical Research Policy and Procedure #401 (Protocol Participant Registration).

12.3 Randomization

Drivers will be randomized to one of the two arms: 1) Driver Wait list control arm or 2) Driver Intervention. After eligibility is confirmed and after consent is obtained, participants will be registered, and then randomized using the MSKCC Clinical Research Database (CRDB) or by calling the MSKCC Clinical Research Administration at [contact] between the hours of 8:30 am and 5:30 pm, Monday - Friday.

13.1 DATA MANAGEMENT ISSUES

The PI and research staff will be responsible for project compliance, data collection, data reporting, regulatory monitoring, problem resolution and prioritization and coordinating the activities of the protocol study team. An RSA will be assigned to the study. The responsibilities of the RSA include project compliance, data collection, abstraction and entry, data reporting, regulatory monitoring, problem resolution and prioritization, and coordination of the activities of the protocol study team.

The data collected for this study will be entered into UNITY Web database, the Department of Psychiatry and Behavioral Sciences secure web-based database application, to be accessed by study staff. The hard copies of the study materials will be

kept in a locked, secured location and will only be accessible to study staff. Participants will be assigned unique identification numbers upon study entry which will be used to identify all the data. Questionnaire may be completed directly online by study staff using tablets, otherwise they will be entered into UNITY Web by research staff on site from hard copy surveys. All hard copy questionnaire data completed by participants will be identified only with a study code number. All data to be analyzed for reporting purposes will continue to be stripped of any identifying information. A list, matching participants' name and case numbers will also be kept in a secure area at MSKCC. All questionnaire data completed by participants will be identified only with a study code number.

The data collected for this study will be managed through UNITY Web Database, questionnaire and screening data will be entered into the research study web based database UNITY maintained by MSKCC. UNITY Web is a secure web based research database application that was developed and being maintained by the MSKCC Department of Psychiatry and Behavioral Sciences. The primary goal of UNITY Web is to streamline research data collection via the Internet and the ease of survey creation.

Data collection in UNITY Web can be accomplished directly over the Internet without establishing a VPN connection. Eliminating the VPN connection requirement can be crucial when conducting multi-site research studies with Institutions outside of MSKCC locations. UNITY Web was developed using the latest Microsoft .Net Framework with C# and JQuery. The application is being hosted by Microsoft IIS and the backend database is on Microsoft SQL Server. A number of various encryption methods were used from the user interface to the servers and as well as the communications between servers. All encryption methods used have either met or exceeded the requirements described in the standard HIPAA web application security guideline.

